A. Study groups - Inclusion criteria

-Patients (males and females) with confirmed Fabry disease (by GLA enzymes and/or DNA testing) naïve and on ERT, mitochondrial diseases (electron transport chain and/or DNA testing) and connective tissue diseases (clinical criteria and/or DNA testing when available)

-Consenting adults and children who are old enough to stand with hands and feet on the Sudoscan plates for at least 2 minutes.

B. Subject population - Exclusion criteria

- In general we exclude potential subjects with cognitive, psychiatric, or other problems that preclude informed consent.

- Patients with history of glucose intolerance or diabetes.

- Patient on chemotherapy

- Other exclusion criteria are:

- People with any open or bleeding wounds at any sensor plate contact surface location
- People with any type of implantable device
- People with missing hand(s) and/or leg(s)
- Pregnant women or women who are uncertain about a possible pregnancy

Study Design

Aim 1.

Analyze electrochemical skin conductance and compare data to SFPN standard of care diagnostic testing (QSRT and skin biopsy) in patients with Fabry disease and evaluate the reliability and sensitivity of SUDOSCAN™ as a new method to assess sweat gland function for the screening of Fabry disease.

- Thirty patients with Fabry disease will be enrolled. Emphasis will be given to treatment-naïve patients but we expect the majority of the patients to be on ERT. We will proactively seek patients who have been on ERT for a short period of time (less than 1 year) and patients who are on ERT with persistent acroparesthesia to maximize the yield of SFPN findings.

- Patients' charts will be reviewed for pertinent medical history, inclusion/exclusion criteria assessment and demographic data (age, gender, body mass index (BMI)). Medications intake will also be reviewed to eliminate patients who are on neurotoxic drug that might cause neuropathies.

- All subjects will receive a complete neurological examination comprising: the neurological symptom score, cranial nerve function, and an evaluation of muscle weakness, muscular atrophy, bilateral reflexes, and sensory function of upper and lower extremities.

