-SUDOSCAN™ will be used on all patients at baseline to collect ESC. A subset of these patients (15) will also undergo standard of care diagnostic testing for SFPN: QSART at the MGH neuromuscular clinic' AFT suit as well as skin biopsy interpreted in [name] [name]'s laboratory. [name] is the director of the neuropathology laboratory and has tremendous expertise in SFPN with normative data for both children and adults¹⁷.

Results of QSRT, skin biopsy and ESC output from SUDOSCAN™ will be compared at baseline.

Aim 2.

Determine whether there is a specific signature pattern of the ESC (intensity, slope and pattern of conductance on the hands and feet) that distinguishes Fabry disease from other disorders causing SFPN such as mitochondrial disease and connective tissue disorders.

- Twenty patients with mitochondrial disease and 15 with connective tissue disease will be enrolled. Patients' charts will be reviewed for pertinent medical history, inclusion/exclusion criteria assessment and demographic data (age, gender, body mass index (BMI)). Medications intake will also be reviewed to eliminate patients who are on neurotoxic drug that might cause neuropathies.

- All subjects will receive a complete neurological examination comprising: the neurological symptom score, cranial nerve function, and an evaluation of muscle weakness, muscular atrophy, bilateral reflexes, and sensory function of upper and lower extremities.

-SUDOSCAN™ will be used on all patients at baseline to collect ESC. A subset of these patients (8 to 10) will also undergo standard of care diagnostic testing for SFPN: QSART at the MGH neuromuscular clinic' AFT suite as well as skin biopsy interpreted in [name] [name]'s laboratory. Results of QSRT, skin biopsy and ESC output from SUDOSCAN™ from each group will be compared to the Fabry patients group to assess for any signature pattern of ESC in Fabry disease.

Study Procedure

1) SUDOSCAN™

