IENFD and sweat gland nerve fiber (SGNF) density evaluations uses a skin biopsy and immunostaining of the tissue to identify and count the intraepidermal and sudomotor nerve fibers. Assessment of nerve fiber density typically involves a 3-mm punch biopsy of skin from the leg (10 cm above the external malleolus). After sectioning by microtome, the tissue is immunostained with anti-protein-gene-product 9.5 (PGP 9.5) antibodies and examined with immunohistochemical or immunofluorescent methods.

Skin biopsy is a well-tolerated procedure and complications which are very rare include: pain, infection, bleeding and delayed healing with scarring.

Primary endpoints

ESC output from SUDOSCAN™. Normative ESC scales previously obtained by Sudoscan™ are provided by the manufacturer for comparison.

Secondary points

1) Specific Fabry disease ESC signature pattern on SUDOSCAN™ testing comparison to other rare diseases with SFPN.

2) ESC characteristics within the Fabry group with assessment of specific phenotypic features of Fabry disease such as disease severity, kidney and cardiac involvement to evaluate any meaningful correlation between the degree of ESC derangement to the disease severity/progression.

Statistical analysis

For a p value <1% at 99.5 power a sample size of 20 patients is sufficient (taking into account standard deviations and data variation from diabetes studies). Multivariate analysis will be used to uncover any ESC variation correlating with the severity of Fabry disease and the different phenotypic variability of the disease.

Anticipated results

We expect SUDOSCAN™ results to be in accordance with the decrease in total sweat response measured by QSART and skin biopsy small fiber neuropathy low density. We expect to see an improvement of ESC in patients on ERT. We expect to see a specific ESC pattern in patients with Fabry disease as compared to other diseases with SFPN.

Potential benefits to society

We anticipate adding to the body of knowledge about SFPN. This method may in time develop into a clinical diagnostic tool with the potential to supplement or replace more arduous tools such as skin biopsy or AFT.

REFERENCES

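### Aim 2 asks whether ESC distinguishes Fabry disease from two other disorders, but the plan only compares groups and includes no measure of discrimination.

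*Combined protocol and SAP*

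**What the plan says.** In the combined protocol and SAP, Aim 2 (under Aims and again under Study Design) looks for an ESC signature, described by intensity, slope and hand/foot pattern, "that distinguishes Fabry disease from other disorders causing SFPN such as mitochondrial disease and connective tissue disorders". The background leading up to the aims likewise speculates that some ESC parameters may discriminate between the three disease groups.

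The planned step comes at the end of Study Design, Aim 2. The QSART, skin biopsy and ESC results of each comparator group "will be compared to the Fabry patients group to assess for any signature pattern of ESC in Fabry disease". No test, feature, cut-off or accuracy measure is named.

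Group sizes: "Thirty patients with Fabry disease will be enrolled" (Aim 1) and "Twenty patients with mitochondrial disease and 15 with connective tissue disease will be enrolled" (Aim 2).

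The list of secondary endpoints repeats the signature without defining it. The Statistical analysis section has two sentences. The first is a sample-size statement, "For a p value <1% at 99.5 power a sample size of 20 patients is sufficient", with the basis given as "taking into account standard deviations and data variation from diabetes studies"; it is tied to no aim or endpoint. The second proposes a multivariate analysis of ESC against severity and phenotype within Fabry disease, which is not a separation of diseases. The ESC limits of 60 and 40 under Study Procedure grade sudomotor dysfunction, not which disease a patient has. Aim 1 mentions sensitivity, but for screening and alongside QSART and biopsy, and also without a method.

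**The concern.** Whether a pattern distinguishes one disease from another is a question about individuals: given a patient's ESC, how well can one say which disease the patient has? A comparison of groups answers a different question, namely whether the distributions differ on average. Two groups can differ beyond reasonable doubt and still overlap so much that the measurement says little about a single patient. This is so even for one feature chosen in advance, with no multiplicity and no chance finding.

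As the plan stands, nothing it would produce separates a useful degree of discrimination from a modest shift with heavy overlap. Either could be described as a Fabry signature. The Anticipated results section already expects a Fabry-specific pattern, so the wording of the conclusion matters.

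**Working it through.** **Inputs from the document.** Fabry n=30, mitochondrial n=20, connective tissue n=15; p<1% and 99.5 power (read as 99.5%), both from the sample-size sentence only.

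**Assumptions, not in the document.** One normally distributed ESC feature, equal SDs, a two-sided test, a cut midway between the group means, and equal weight for both groups. Differences d are in SD units.

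**1. The plan's own figure.** The 20 patients cannot be reproduced, because no effect size or SD is given. Working backwards, z(0.995) + z(0.995) = 2.576 + 2.576 = 5.152, so the implied difference is:
- one sample of 20: 5.152 × √(1/20) = 1.15 SD
- 20 per group: 5.152 × √(2/20) = 1.63 SD
- 10 per group: 5.152 × √(2/10) = 2.30 SD

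The document does not say which is meant. On the 20-per-group reading, d = 1.63 corresponds to an AUC of Φ(1.63/√2) = 0.875 and misclassification of Φ(−1.63/2) = 21%.

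**2. Smallest observed difference that reaches two-sided p=0.01.** d = t(0.995, n1+n2−2) × √(1/n1 + 1/n2).
- 30 v 20: 2.682 × 0.289 = 0.774
- 30 v 15: 2.695 × 0.316 = 0.852

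**3. What that difference means for individual patients.**

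| Quantity | Formula | 30 v 20 | 30 v 15 |
|---|---|---|---|
| AUC | Φ(d/√2) | 0.708 | 0.727 |
| Misclassified at midpoint cut | Φ(−d/2) | 34.9% | 33.5% |
| Sensitivity at 90% specificity | Φ(d − 1.2816) | 30.6% | 33.4% |

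If the test were one-sided, the misclassified shares at the boundary would be 36.4% and 35.1%.

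**4. Could a weak separator reach that level?** With a true d of 0.87, which misclassifies 33%, the noncentral t gives a probability of reaching p<0.01 of 63% (30 v 20) and 53% (30 v 15).

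**5. Precision of the AUC at these sizes.** Hanley–McNeil: SE² = [A(1−A) + (m−1)(Q₁−A²) + (n−1)(Q₂−A²)]/(mn), with Q₁ = A/(2−A), Q₂ = 2A²/(1+A), m = 30.
- 30 v 20, A = 0.708: SE 0.073, 95% CI 0.708 ± 1.96 × 0.073 = 0.57 to 0.85
- 30 v 15, A = 0.727: SE 0.076, 95% CI 0.727 ± 1.96 × 0.076 = 0.58 to 0.88

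**The case against.** Several points count against pressing this further.

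- **A reader might infer that p<1% is the plan's test for declaring a signature.** It is not. It stands only in the sample-size sentence, about 20 patients, and is assigned to no aim. Aim 2 has no stated criterion. The 1% level serves here only to illustrate.
- **A reader might infer that Aim 2 will misclassify a third of patients.** The document supports no such forecast. It does not say that means are compared, and it speaks of a pattern over several features. A combination might separate the groups better than one feature, and a true difference well above the boundary would do so as well. The figure describes one feature at exactly p=0.01.
- **A reader might link this to the hope, under Potential benefits to society, that the method becomes a diagnostic tool.** That sentence is about supplementing or replacing skin biopsy or autonomic testing, that is, diagnosing small-fibre neuropathy. It is not about telling Fabry disease from the comparators.
- **The study calls itself preliminary, and the signature is a secondary endpoint.** A pass/fail AUC limit would therefore be a confirmatory standard that the design was not built for. For instance, suppose the lower 95% limit had to exceed 0.70 against both comparators. In a simulation under the same normal model with Hanley–McNeil limits, this happens in about 35% of studies when the true d is 1.3 (AUC 0.82), and in about 8% when it is 1.0 (AUC 0.76).

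All four stand as limits on the point. None of them supplies a measure of discrimination, and exploratory status does not remove the need for one: an estimate of separation with its uncertainty is what a preliminary study of this question can usefully deliver.

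**Conclusion.** The point holds in a limited form: the aim is about discrimination, the planned step is a group comparison, and no planned quantity links the two. Under the assumptions listed in the working, a difference just significant at the 1% level leaves roughly one patient in three on the wrong side of a midpoint cut, so significance alone could not support the word distinguishes. The gap itself does not depend on those assumptions; only its illustrated size does. It deserves correction before analysis, with modest weight because it concerns a secondary endpoint of a preliminary study.

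**What to change.** In Study Design, Aim 2 and in Statistical analysis, make discrimination the Aim 2 measure:

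- Report the AUC with 95% CI and the sensitivity at a fixed specificity (for example 90%), separately for Fabry v mitochondrial and Fabry v connective tissue disease.
- Do this for an ESC feature named in advance. If features are selected or combined on the study data, use cross-validation that includes the selection step; otherwise the AUC will be too favourable.
- Say how the fixed specificity is set in small groups. With 15 comparators the observed specificity moves in steps of 1/15 = 6.7%, so exactly 90% cannot be observed: 13/15 is 86.7% and 14/15 is 93.3%.
- Describe a group difference without this evidence as a difference in ESC, not as a signature that distinguishes Fabry disease.

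No fixed AUC threshold is needed.

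**Cost.** Changes of wording and a little more analysis on data already to be collected; no added patients, visits or tests. The drawback is that the intervals will be wide, as shown in the working, and any claim will look less certain. At these group sizes that is a fair picture of what the study can show.

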In the Neuro-genetics unit at the Massachusetts General Hospital (MGH), we also follow hundreds of patients with rare diseases such as mitochondrial disease and connective tissue disorders. Despite the variable pathophysiology of these disorders SFPN seems to be a common pathogenic pathway shared with Fabry disease and leading to the same multiple complaints from the patients. In mitochondrial disease, SFPN is thought to be the result of lack of energy production and abnormal nerve metabolism, whereas in connective tissue disease, the abnormal structural proteins within the tissues are likely the cause. Because of these very different mechanisms and the fact that Sudoscan may be more sensitive to subtle SFPN changes, one might speculate that there are possibly discriminating ESC parameters (intensity, slope and pattern of conductance on the hands and feet) that might be able to distinguish SFPN within these 3 disease groups.

Thus we seek to find faster, less-invasive ways to diagnose and monitor small-fiber polyneuropathy in Fabry disease as well as identify a signature pattern of Fabry-induced SFPN in comparison to other rare diseases. Since Sudoscan measurement is non-invasive and takes only 2 minutes, it is an attractive potential add-on to the routine clinical care of our patients.

Aims:

The aims of this preliminary study are to:

Aim 1.

Analyze electrochemical skin conductance and compare data to SFPN standard of care diagnostic testing (QSRT and skin biopsy) in patients with Fabry disease and evaluate the reliability and sensitivity of SUDOSCAN™ as a new method to assess sweat gland function for the screening of Fabry disease.

Aim 2.

Determine whether there is a specific signature pattern of the ESC (intensity, slope and pattern of conductance on the hands and feet) that distinguishes Fabry disease from other disorders causing SFPN such as mitochondrial disease and connective tissue disorders.

Methods

Study population

Adults and children ages 4 to 65 years recruited at MGH Neurogenetics clinic. If local recruitment is incomplete, advertisement will be made on patient support groups for broader national patients' enrollment. Informed consent will be obtained from all participants prior to the measurement with SUDOSCAN™. Young participants age 17 and below will provide Assent in addition to Consent from their parents.

Submission to the Institutional Review Board (IRB) for this protocol will be initiated once this proposal has been approved.

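### Does the 20-patient, 99.5% power statement fail because the comparison of ESC with QSART and skin biopsy has only 15 Fabry patients?

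*Combined protocol and SAP*

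**What the plan says.** The Statistical analysis section contains the only sample-size statement in the text available: "For a p value <1% at 99.5 power a sample size of 20 patients is sufficient". In support it refers only to standard deviations and variation seen in diabetes studies. It gives no value for either, and no contrast, test or sidedness.

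The Primary endpoints section lists ESC output alone and adds: "Normative ESC scales previously obtained by Sudoscan™ are provided by the manufacturer for comparison".

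Under Study Design, Aim 1, "Thirty patients with Fabry disease will be enrolled", and "A subset of these patients (15) will also undergo standard of care diagnostic testing for SFPN". These results are then set side by side: "Results of QSRT, skin biopsy and ESC output from SUDOSCAN™ will be compared at baseline". The aim itself is partly to "evaluate the reliability and sensitivity of SUDOSCAN™ as a new method to assess sweat gland function for the screening of Fabry disease". The inclusion criteria admit Fabry patients "with confirmed Fabry disease (by GLA enzymes and/or DNA testing").

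Under Aim 2, 20 patients with mitochondrial disease and 15 with connective tissue disease are enrolled.

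The Anticipated results section expects agreement in direction: "We expect SUDOSCAN™ results to be in accordance with the decrease in total sweat response measured by QSART", and likewise with low fibre density on biopsy. The Aims section calls the study preliminary.

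**The concern.** A reader who meets a single, unqualified power statement will tend to apply it to the first aim. That aim compares ESC with the reference tests in 15 Fabry patients, five fewer than the number called sufficient. The quantities of interest there (agreement, sensitivity) are also not a mean difference of the kind that SDs from diabetes studies would size. On that reading the protocol promises 99.5% power where it has not shown it.

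The target of the sensitivity in Aim 1 is also open. It could be small-fibre polyneuropathy as shown by biopsy or QSART, with at most 15 Fabry patients in the denominator. It could instead be Fabry disease itself, with all 30. No precision is stated for either.

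At stake is how much weight the 15-patient comparison can bear, given the protocol's hope that the method may one day supplement or replace biopsy and autonomic testing.

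**Working it through.** **Can the 20 be reproduced?** Inputs from the Statistical analysis section: alpha 0.01, power 0.995, n = 20. Difference, SD, test, sidedness and design are not given, so a forward calculation is impossible. The most that can be done is to solve for the standardised effect d that makes 20 exactly the number needed. All effects below are therefore implied or assumed, not taken from the documents. Tests are two-sided at 1%.

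Normal approximation, one sample or pairs: d = (z for 0.995 + z for 0.995)/√n = (2.576 + 2.576)/√20 = 5.152/4.472 = 1.15. The noncentral t gives the slightly larger values used from here on:

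| Reading of 20 | Implied effect |
|---|---|
| One sample or pairs | d = 1.27 |
| Two groups of 20 | d = 1.71 |
| 20 in total, 10 per group | d = 2.55 |
| Correlation, 20 pairs (Fisher z) | r = tanh(5.152/√17) = 0.85 |

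The figure of 20 can be reached under several designs. It is neither confirmed nor refuted.

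**Primary ESC endpoint against norms, 30 Fabry patients.** At the one-sample effect d = 1.27, power with n = 30 exceeds 99.9%. The plan more than meets its own figure here.

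**If the sentence were applied to the 15 patients with QSART and biopsy.**
- One-sample or paired reading, d = 1.27: power at n = 15 is 95.8%.
- Correlation reading, r = 0.85: power = Φ(atanh(0.848)·√12 − 2.576) = Φ(1.752) = 96.0%.
- The effect at which n = 15 itself gives 99.5% is d = 1.52, or r = 0.90.
- With weaker assumed correlations, power at 15 pairs is 67% at r = 0.7 and 43% at r = 0.6.

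Power at 15 is thus unknown. Saying that 20 is sufficient does not say that 20 is the minimum, and no effect is stated for this comparison.

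**ESC between disease groups (Aim 2).**

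| Reading of 20 | 30 v 20 | 30 v 15 |
|---|---|---|
| One sample, d = 1.27 | 95% | 90% |
| 20 per group, d = 1.71 | 99.9% | 99.5% |
| 20 in total, d = 2.55 | above 99.99% | above 99.99% |

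Whether these reach 99.5% depends wholly on which reading is chosen.

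**Precision of sensitivity (exact Clopper-Pearson 95% CI).** When all n are detected, the lower limit is 0.025^(1/n). The observed counts are assumptions.

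| Target | Detected | 95% CI |
|---|---|---|
| Neuropathy, all 15 reference-positive | 15 of 15 | 78% to 100% |
| Neuropathy, all 15 reference-positive | 12 of 15 | 52% to 96% |
| Neuropathy, only 10 reference-positive | 10 of 10 | 69% to 100% |
| Fabry disease itself | 30 of 30 | 88% to 100% |
| Fabry disease itself | 24 of 30 | 61% to 92% |

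The first two rows are best cases for width, because the plan does not say that all 15 will be positive on the reference tests.

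**The case for a change.** The strongest argument for a change is that it would cost one paragraph and no patients: name the sized comparison, say which sensitivity is meant, and declare the 15-patient comparison to be estimation. The sentence is indeed attached to nothing. The 20 equals only the size of the mitochondrial group, to which the text does not link it. The sentence cannot be reproduced and should not be cited as evidence of power against QSART or biopsy. All of that stands.

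It does not amount to a fault that affects the results. The protocol nowhere claims 99.5% power for the reference-test comparison, which is not listed among the primary or secondary endpoints. Showing that a figure is unproven for a comparison it was never said to cover does not show that the figure is wrong.

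The obvious remedy also brings problems of its own. Printing 78% to 100% as the precision for the 15 patients assumes that every one is reference-positive, which would overstate it. Prescribing sensitivity and percentage agreement makes the comparison binary, although total sweat response and fibre density are quantitative. No positivity rule is given for either test, and nothing says which governs if they disagree. And confining the 99.5% to a named comparison, without its difference and SD, would leave it just as irreproducible.

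**Conclusion.** The concern identifies missing detail, not an error that calls for a change. On the natural reading of the sizing sentence (the primary ESC endpoint against norms), 30 patients exceed the 20 required. If the sentence is instead stretched to the 15-patient comparison, the fall is from 99.5% to about 96% when 20 was exactly the number needed, and there is none at d of about 1.52 or more. Power could be much lower for a modest correlation, but no stated effect makes that a broken promise. These values assume two-sided tests at 1% and effects back-solved from n = 20.

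The real limit is precision: with at most 15 reference-positive Fabry patients, even perfect detection leaves sensitivities down to 78% inside the interval. That is a fair trade-off in a study that calls itself preliminary and proposes replacement of biopsy only as a possible later development. An analyst following the plan can report the association of ESC with the quantitative reference measures. Where a positivity rule is defined, sensitivity can be reported with an exact interval on the actual number of reference-positive patients, with its target stated. No result becomes unsound if the protocol stands as written, provided nobody quotes 99.5% for the comparison with QSART and biopsy.
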